Study Protocol and Statistical Analysis Plan: Cultivating Gratitude: Does Manipulating
Expectations Improve the Efficacy of a Gratitude Intervention?

NCT03784001

January 10, 2019

Cultivating Gratitude: Does Manipulating Expectations Improve the Efficacy of a Gratitude Intervention?

Interventions designed to elicit gratitude, an emotion expressed when one feels they have received something beneficial from other people or entities (Emmons & McCullough, 2003), have been shown to positively affect psychological and physical well-being. In previous studies, participants instructed to cultivate feelings of gratitude reported reductions in stress (i.e., O'Leary & Dockray, 2015) and increases in life satisfaction (e.g., Emmons & McCullough, 2003, study 1; Froh, Sefick, & Emmons, 2008; Khanna & Singh, 2016; and Gilek, 2010; Kerr, O'Donovan, & Pepping, 2015), positive mood (e.g., Emmons & McCullough, 2003, study 2; Martínez-Martí, Avia, & Hernández-Lloreda, 2010; Khanna & Singh, 2016; and Froh et al., 2014, study 2), and well-being (e.g., Khanna & Singh, 2016; Deng et al., 2019; and Jachowska, Brown, Ronaldson, & Steptoe, 2015) (e.g. Froh, Sefick, & Emmons, 2008; Emmons & McCullough, 2003; Watkins, Woodward, Stone, & Kolts, 2003, study 3, study 4). Though gratitude interventions are widely used, there are very few studies that examine whether small additions to methodology can enhance the effectiveness of these interventions. Drawing from literature on mindset and the placebo effect, we hypothesized that providing participants with information about the positive effects of previous gratitude interventions would improve their well-being, mood, and sleep after participating in a gratitude intervention.

The majority of randomized controlled trials (RCTs) designed to cultivate gratitude report beneficial outcomes, though these effects are typically small. Evidence from studies on mindset and expectations suggest that these effects may be enhanced, though few studies have tested this. Research on mindset - conscious or embodied expectation (Crum, Leibowitz, &

Verghese, 2017)- and the placebo effect indicates that individuals may experience greater health improvements when they know the benefits of a job or activity (e.g., Crum & Langer, 2007; Desharnais, Jobin, Côté, Lévesque, & Godin, 1993). In one study, for example, hotel maids who were told how many calories each of their job tasks burned and informed that their work met the requirements for good exercise and an active lifestyle exhibited significant health improvements--reduced weight, blood pressure, and body fat--when compared to hotel maids who were not provided with this information (Crum & Langer, 2007). In another study, participants who were told that an exercise program was meant to improve psychological well-being showed significant improvements in well-being relative to uninformed participants (Desharnais, Jobin, Côté, Lévesque, & Godin, 1993). These studies suggest that knowing the benefits of an activity beforehand can enhance beneficial effects.

Indeed, motivation and participant engagement are important factors in intervention efficacy (Lyubomirsky & Layous, 2013). Being motivated to first begin, and then continue to put effort into, a positive intervention can enhance intervention benefits. Participants who chose to engage in (and actually received) a “happiness” intervention (either promoting optimism or gratitude) experienced the greatest increases in happiness; of those receiving a happiness intervention, participants who put the most effort into their intervention’s exercises had the greatest gains in well-being (Lyubomirsky, Dickerhoof, Boehm, & Sheldon, 2011). Similarly, there is some evidence that reading encouraging information about an intervention improved outcomes. In an intervention in which the experimental conditions wrote about their best possible selves - their goals in different domains of life - participants who read peer testimonies about the effectiveness of the intervention had greater improvements in well-being than participants who

read unrelated testimonies and participants in the control condition (Layous, Nelson, & Lyubomirsky, 2012).

To our knowledge, only two gratitude interventions have tested outcome differences between informed (of benefits of gratitude interventions) versus not informed conditions. In one intervention, one gratitude condition was assigned to read fake articles about gratitude practices being effective. These participants experienced decreased well-being (at post-intervention), then increased well-being (at a three-week follow-up) compared to participants who read articles about gratitude practices being ineffective (Sin, Della Porta, & Lyubomirsky, 2011). These results do not clearly indicate if it is beneficial to advertise intervention efficacy, and utilized fake testimonies for encouragement. Harbaugh and Vasey (2014) had one gratitude condition read a short paragraph explaining the rationale for the intervention which concluded with the statement, “Filling out the following questionnaire is expected to have a positive effect on your well-being”. Participants were shown this rationale at the beginning of their instructions for every writing session, but did not experience better outcomes than the gratitude condition not shown the rationale (Harbaugh & Vasey, 2014). This finding may indicate that providing encouraging information about gratitude does not enhance intervention effectiveness. However, informed participants in Harbaugh and Vasey (2014) were only told one general benefit of gratitude. The present study told participants six specific, favorable outcomes from past gratitude studies. This design was intended to remind participants of intervention benefits each time they made a gratitude list, and was predicted to significantly improve participant’s outcomes.

The present study sought to determine whether telling participants the benefits of gratitude exercises would improve the effectiveness of a two-week gratitude intervention.

Participants were randomized to one of three conditions: gratitude + expectations (GE), gratitude + no expectations (GNE), or events control. Participants in the GE condition were shown a beneficial outcome from a past gratitude study each time they made a gratitude list; those in the GNE condition were not. Based on studies in which participants experienced improved health and well-being when they knew the benefits of an activity (e.g., Crum & Langer, 2007; Desharnais, Jobin, Côté, Lévesque, & Godin, 1993), we hypothesized that participants in the GE condition would experience the greatest improvements in outcomes. Our primary outcome was well-being and our secondary outcomes were positive affect, sleep quality, sleep quantity, gratitude, stress, and depressive symptoms. We hypothesized that, compared to the control and GNE conditions, (1) the GE condition would report the greatest increases in hedonic, eudaimonic, and overall well-being and (2) the GE condition would report the greatest gains in positive affect, sleep quality, sleep quantity, and gratitude, and the greatest reductions in stress and depressive symptoms.

Method

Participants and Procedure

Participants were recruited from an undergraduate psychology class at a large, public university. Inclusion criteria were being 18 years or older and having access to an email account. The study was announced to all 197 students in-person by the professor and via email. Study participation was offered as an alternative to completing one of the six class writing assignments, which were of comparable effort and time investment to study activities. All students were emailed a study information sheet. Students had to affirm that they met inclusion criteria and electronically sign and date the information sheet to enroll in the study. One hundred and

twenty-nine participants elected to enroll in the study by submitting a signed information sheet. All study procedures were approved by the University of California, Los Angeles Institutional Review Board and consent was obtained from participants. The ClinicalTrials.gov identifier for this trial is NCT03784001.

Participants were randomly assigned to one of the three conditions (GNE, GE, or events control) using a random number generator. On the first day of the study, participants received a baseline questionnaire via email. After completing their baseline questionnaire, participants were prompted to an online form, with instructions to type a short list, specific to the condition they were in (see *Interventions* below for more information). Every two days, participants were emailed a link to a new condition-specific online form. In total, participants were instructed to complete six condition-specific lists. Participants were emailed their post-intervention questionnaire two weeks after they received their baseline questionnaire. Participants received a reminder email to complete their baseline and post-intervention questionnaire if they did not complete either questionnaire one day after dissemination.

Interventions

Participants received an email with a link to each list, sent two days after completion of the previous list. GNE participants were instructed to list up to five things they were grateful for; GE participants were shown positive findings from gratitude RCTs and were instructed to list up to five things they were grateful for. Participants in the events control condition were instructed to list up to five events they engaged in that day.

Both gratitude conditions (GNE and GE) were given the following instructions, adapted from Emmons and McCullough (2003) and Sheldon and Lyubomirsky (2006):

You have been randomly assigned to try to cultivate a sense of gratitude now, and during the next few weeks. There are many things in our lives, both large and small, that we might be grateful about. These might include particular supportive relationships, sacrifices or contributions that others have made for you, facts about your life such as your advantages and opportunities, or even gratitude for life itself, and the world that we live in. Think back over the past day and, on the lines below, type up to five things in your life that you are grateful or thankful for.

GE participants were also shown a beneficial finding about gratitude on each of their questionnaires, immediately before they made their gratitude list. Some of the beneficial findings included: “*Undergraduates who practiced gratitude had higher expectations for the upcoming week (Emmons & McCullough, 2003, Study 1)*” and “*Gratitude contemplation can decrease body dissatisfaction and increase body esteem (Wolfe & Patterson, 2017)*”.

Participants in the events condition were given the following instructions:

You have been randomly assigned to write about your daily events now and over the next two weeks. Throughout a day, we may engage in many different events. These might include classes you had today, conversations you had, or activities you engaged in such as studying for a test or eating a meal. Many events happen throughout a day. Think back over your activities today and, in the space below, type up to five things or events you remember from today.

Measures

Demographic characteristics. Demographic variables - age, sex race, year in school, major, relationship status, and family income - were assessed at baseline.

Primary outcomes. Hedonic well-being, eudaimonic well-being, and overall well-being were assessed at baseline and post-intervention. Well-being was measured with the Mental Health Continuum-Short Form (MHC-SF; Keyes, 2009). Participants rated how often they felt 14 different emotions or statements, such as “happy” and “satisfied with life”. Items are rated on a 6-point likert scale (0 = *never*, 5 = *everyday*), with higher numbers indicating greater well-being. This measure assesses both hedonic and eudaimonic well-being. The MHC-SF is both reliable and valid for use with young adults (Robitschek & Keyes, 2009) .

Secondary outcomes. Positive affect, sleep quality, sleep quantity, gratitude, and the greatest reductions in stress and depressive symptoms were assessed at baseline and post-intervention.

Statistical Analysis Plan

Differences in demographic variables were assessed using one-way Analysis of Variance (ANOVA) and chi-squared tests to examine baseline differences between groups. Next, for each primary (i.e., well-being) and secondary outcome (i.e., positive affect, sleep quality) we ran separate repeated measures ANOVAs using SPSS. Differences in change over time between groups were assessed using the time-by-condition interaction term, which tells us whether groups differed over time for each outcome. Post hoc analyses were then conducted to further investigate any significant interactions. Finally, to test if completing the gratitude exercises improved well-being, we combined the GE and GNE conditions to create a combined gratitude (CG) group which we compared to the control condition. To do this, we ran separate repeated measures ANOVAs comparing the CG group to the control condition, looking at the time-by-condition interaction term for each outcome.

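### Do the two descriptions of when list links were emailed, set against a fixed two-week questionnaire, call for a change to the plan?

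*Combined protocol and SAP*

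**What the plan says.** The Participants and Procedure section sets out the schedule in outline. List 1 follows directly on the baseline questionnaire. After that, "Every two days, participants were emailed a link to a new condition-specific online form". The number is given as well: "In total, participants were instructed to complete six condition-specific lists". The only follow-up assessment is dated from baseline and not from the lists: "Participants were emailed their post-intervention questionnaire two weeks after they received their baseline questionnaire". Reminders are described for the two questionnaires: "Participants received a reminder email to complete their baseline and post-intervention questionnaire if they did not complete either questionnaire one day after dissemination". None is described for the lists.

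That section refers the reader to the Interventions section for detail on the lists, where the spacing is put differently: "Participants received an email with a link to each list, sent two days after completion of the previous list".

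The lists also carry the experimental message. The introduction says: "Participants in the GE condition were shown a beneficial outcome from a past gratitude study each time they made a gratitude list". It presents the number of messages as an advance on an earlier study that gave one general benefit: "The present study told participants six specific, favorable outcomes from past gratitude studies".

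**The concern.** Taken literally, one sentence describes a calendar interval and the other a trigger that depends on the participant. They give the same dates only when every list is done on the day it arrives. Under the trigger wording, delays add up while the questionnaire date stays fixed. A slow participant could therefore be assessed before being sent list 6. A participant who skips a list would, on a literal reading, have nothing to set off the next one.

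For the gratitude + expectations arm, each list not reached is also a benefit statement not seen. If this were common, the trial would be testing fewer than the six statements on which the introduction builds its case. The contrast with gratitude without expectations, and the contrast of gratitude with control, could both be diluted. The Statistical Analysis Plan describes the pooled comparison as made "to test if completing the gratitude exercises improved well-being", yet plans no count of lists completed.

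**Working it through.** **Inputs, all from Participants and Procedure or Interventions.** Six lists; two-day spacing; list 1 at the baseline session (day 0 if baseline is done on the day it is received); questionnaire emailed on day 14.

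**Calendar wording.** List k is sent on day 2(k − 1), which gives days 0, 2, 4, 6, 8, 10. Slack before the questionnaire: 14 − 10 = 4 days. The stated programme fits within two weeks.

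**Trigger wording.** Let d_j be the days from receipt of list j to its completion. List k is sent on day 2(k − 1) + d_1 + … + d_(k−1), so list 6 is sent on day 10 + D, with D = d_1 + … + d_5.

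- No delay, D = 0: day 10, the same as the calendar wording.
- Lists 2 to 5 each one day late, D = 4: day 14, the day of the questionnaire.
- Lists 1 to 5 each one day late, D = 5: the links go out on days 0, 3, 6, 9, 12, 15. List 6 misses the questionnaire by one day, and five of six lists are sent before it.
- Lists 1 to 5 each two days late, D = 10: days 0, 4, 8, 12, 16, 20. Four of six lists are sent before it.

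List 6 is sent after day 14 exactly when D exceeds 4 days. If one of lists 1 to 5 is never completed, the text states no rule for what happened next.

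**How often?** The documents give no completion times and no skip rates, so this cannot be computed. Assumed exponential delays show how far the answer depends on the input. The chance that D exceeds 4 is the upper tail of a gamma distribution with shape 5 and scale equal to the mean delay. For a mean delay of 0.25 day it is 0.04%; for 0.5 day, 10%; for 1.0 day, 63%. Even at a mean of 1.0 day, the expected number of lists sent by day 14 is 5.2 of 6. The frequency is therefore open, and delay alone typically costs about one list.

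**What it does to the comparison.** The same rule applies in all three arms, so it creates no imbalance by design. If participants in one arm completed lists faster, that would be a consequence of assignment and part of what a comparison by assigned arm measures. Reduced exposure would be expected to shrink a true difference, not to create a false one. The planned repeated measures ANOVAs are the same under either wording.

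**The case for a change.** The strongest argument for acting is that the fixed questionnaire date is a difficulty even if the two sentences describe one rule. The trigger wording alone permits an assessment before list 6, and the number of statements seen is central to the study's rationale. Clarifying the wording and tabulating lists completed by arm would cost almost nothing, and it would show readers what exposure was compared.

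The arithmetic behind this stands: late sending is possible and its frequency is unknown. Three parts carry less weight.

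- That list 6 might never be sent is inferred from silence. No sentence says that a missed list ended the mailings, and an unstated fallback cannot be excluded.
- The pooled gratitude analysis cannot bear on whether the message was delivered, because it combines the arms with and without the message. The message is tested in the three-group time-by-condition interaction and its post hoc comparisons.
- The lack of a planned list count does not come from the inconsistency. Under the calendar wording too, a list can be skipped, or sent on day 10 and completed after day 14. Neither wording guarantees six completed lists.

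What remains is a case for clear reporting. A table of lists completed by arm is a sensible addition that an analyst would normally supply from the online forms, and it alters no test.

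**Conclusion.** No change to the plan follows. The outline paragraph sends the reader to the Interventions section, so its two-day interval can be read as a summary of the fuller sentence. This note does not decide which rule was operated. The two sentences still need to be reconciled with each other and with the two-week questionnaire date when the trial is reported, and that is for the sponsor. The procedures are described in the past tense, so nothing remains to be rescheduled.

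The size is bounded by the day arithmetic: 4 days of slack, list 6 late only if total delay over five lists exceeds that, and five of six lists sent in time if every list is one day late. The likely effect is some dilution of exposure, common to all arms by design, and not bias. This rests on list 1 being done at the baseline session and on comparison by assigned arm. It would weigh more if many participants had stopped receiving lists early, but the documents give no sign of that.

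### With only two time points the repeated measures ANOVA is a change-score test; adjusting for baseline would sharpen every comparison at almost no cost

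*Combined protocol and SAP*

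**What the plan says.** Under Measures, the primary outcomes have two assessments: "Hedonic well-being, eudaimonic well-being, and overall well-being were assessed at baseline and post-intervention". The secondary outcomes have the same two: "Positive affect, sleep quality, sleep quantity, gratitude, and the greatest reductions in stress and depressive symptoms were assessed at baseline and post-intervention". No other assessment time is described for any outcome.

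The Statistical Analysis Plan says of the outcomes that "we ran separate repeated measures ANOVAs using SPSS", and then: "Differences in change over time between groups were assessed using the time-by-condition interaction term". Post hoc analyses follow where that interaction is significant. The two gratitude arms are then pooled and analysed in the same way: "we ran separate repeated measures ANOVAs comparing the CG group to the control condition".

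No model includes the baseline score of the outcome as a covariate. The only baseline comparisons described concern demographic variables.

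Two further facts matter. Allocation was random: "Participants were randomly assigned to one of the three conditions (GNE, GE, or events control) using a random number generator". And the baseline questionnaire was completed before the first condition-specific list (Participants and Procedure), so the baseline score cannot have been affected by the condition.

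**The concern.** A change score subtracts the whole of the baseline value. That is the most precise use of baseline only when the regression slope of post on baseline equals 1. With imperfect correlation and similar SDs the slope is below 1, so subtraction over-corrects and carries baseline noise into the contrast. A baseline-adjusted model (ANCOVA) estimates the slope instead.

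The introduction describes the effects of gratitude interventions as mostly small, and enrolment ended at 129 students across three arms. The comparison of gratitude + expectations (GE) with gratitude + no expectations (GNE) carries the main hypothesis, and it uses only about two thirds of them. Precision that can be had from data already in hand is worth taking. Validity is not at stake, and chance baseline imbalance is not a separate harm: it is the source of the extra variance calculated here.

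**Working it through.** The plan contains no sample-size calculation, power, SD or correlation, so there is no figure of its own to reproduce.

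**Inputs from the documents.** Three randomised arms; 129 enrolled; two assessments per outcome; time-by-condition interaction as the test.

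**Assumed.** 43 per arm (129/3, as no allocation ratio is given); complete pairs; two-sided 5% level; a common slope across arms; ρ from 0.4 to 0.8; k = post SD / baseline SD of 0.8, 1.0 or 1.2. Effects are in baseline SDs.

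**Step 1: the planned test is a change-score test.** On a simulated data set of 3 × 43 participants with two times, the split-plot interaction F and the one-way ANOVA F on post minus baseline were both 0.40526, with 129 − 3 = 126 error df.

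**Step 2: error variances, in units of baseline variance.**
- Change score: 1 + k² − 2ρk
- ANCOVA: k²(1 − ρ²)
- Difference: (1 − ρk)², which is never negative

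With k = 1 the ratio is (1 − ρ²)/[2(1 − ρ)] = (1 + ρ)/2, so the fractional cut is (1 − ρ)/2. At ρ = 0.5 the variances are 1.00 and 0.75, a cut of 25%.

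**Step 3: cost of estimating the slope.** ANCOVA variance is inflated by about 1 + 1/124 = 1.008. At ρ = 0.5 and k = 1 the net cut is 1 − 1.008 × 0.75 = 24.4%. Net cuts over the grid:

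| k | ρ = 0.4 | 0.5 | 0.6 | 0.7 | 0.8 |
|---|---|---|---|---|---|
| 0.8 | 46% | 42% | 39% | 37% | 35% |
| 1.0 | 29% | 24% | 19% | 14% | 9% |
| 1.2 | 18% | 12% | 7% | 3% | −0.5% |

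**Step 4: what this means for the comparisons (k = 1).** For GE v GNE the standard error is √(variance × 2/43). At ρ = 0.5 this is √(1.00 × 2/43) = 0.216 for change and √(0.75 × 1.008 × 2/43) = 0.188 for ANCOVA. Power is from the noncentral t, with 126 df (change) and 125 df (ANCOVA). For combined gratitude (86) v control (43) the df are 127 and 126 and the factor is 1 + 1/125. Each cell gives change v ANCOVA.

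| | ρ = 0.5 | ρ = 0.6 | ρ = 0.7 |
|---|---|---|---|
| GE v GNE, 95% CI half-width (SD) | 0.43 v 0.37 | 0.38 v 0.34 | 0.33 v 0.31 |
| GE v GNE, power at 0.2 SD | 15.1 v 18.5% | 17.7 v 20.9% | 22.1 v 25.0% |
| GE v GNE, power at 0.4 SD | 45.3 v 56.2% | 53.9 v 63.0% | 66.1 v 72.8% |
| Combined v control, power at 0.2 SD | 18.6 v 23.1% | 22.1 v 26.3% | 27.9 v 31.7% |
| Combined v control, power at 0.4 SD | 56.6 v 68.6% | 66.1 v 75.4% | 78.3 v 84.2% |

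The GE v GNE powers are for the contrast on its own, without first requiring a significant three-arm interaction.

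**Step 5: simulation check.** In 20,000 simulated trials of 3 × 43 per setting (k = 1.0 and 1.2), type I error was 4.6–5.1% for both tests, and both mean estimates were within 0.006 SD of the true effect. Simulated variance cuts for ρ = 0.4 to 0.8 were 29, 24, 20, 14 and 9% (k = 1) and 19, 12, 7, 2 and 0% (k = 1.2), in line with the formula.

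**The case against.** The planned test is valid, and it speaks directly to the hypothesis that "the GE condition would report the greatest increases in hedonic, eudaimonic, and overall well-being". On this view baseline adjustment is a preference and corrects no error. That is true as far as it goes: the point is one of efficiency. But under randomisation both analyses estimate the same between-arm effect, so the hypothesis about increases is answered equally well by the more precise one.

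The size of the gain cannot be read from the documents, and one cell of the grid shows a loss. Both are true; the loss is 0.5%.

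The gain is modest where effects are small. At 0.2 SD, GE v GNE power rises by only about 3 percentage points. This stands: adjustment narrows the interval but does not make a small GE–GNE difference well powered. The 0.4 SD figures are illustrative, as the documents give no effect size.

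The plan looks at pairwise differences only after a significant three-arm interaction. With that gate applied in simulation (effect in GE only, ρ = 0.5, 0.4 SD), GE v GNE power is about 36–37% v 48%, not 45% v 56%. The absolute powers in the table are therefore too high for the plan as written, but the gap between methods is similar. The variance cut does not depend on the gate. Incomplete pairs would also lower every power figure.

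The guarantee of no large-sample loss assumes a common slope. With equal SDs and slopes of 0.9, 0.9 and 0.5 in GE, GNE and control, the pooled slope is 0.767. The GE–GNE variance is then 1 + 0.767² − 2 × 0.767 × 0.9 = 0.208, against 0.200 for change scores: a loss of about 4%, or 5% with the slope-estimation cost. Slopes have to differ sharply for this to happen.

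Finally, the text is in the past tense, so changing the model now could be a post hoc switch. This bears on how the fix is made, not on whether the point holds.

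**Conclusion.** The point holds. The documents describe two assessments per outcome and no baseline-adjusted model, so the analysis is a change-score ANOVA that gives up precision already paid for. With equal SDs the net loss is about 24% of contrast variance at ρ = 0.5 and 14% at ρ = 0.7. Put another way, 129 participants analysed with adjustment are worth 129/0.756 ≈ 171 under the change-score analysis at ρ = 0.5, and 129/0.857 ≈ 151 at ρ = 0.7.

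The algebra is certain. The size rests on assumed ρ, SD ratio, 43 complete pairs per arm and a common slope. Across the assumed grid it runs from a 46% gain to a 0.5% loss. The change should be made, but the planned analysis is not invalid without it.

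**What to change.** For each outcome, model the post-intervention score on assigned condition plus the baseline score of the same outcome. Take the GE–GNE and GE–control contrasts from that model, and use the same form for combined gratitude v control. State whether the pairwise contrasts still wait for a significant overall test of condition; adding the covariate does not require that rule to change.

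A two-time-point mixed model with a common baseline mean across arms is an alternative. It also keeps participants who have only one of the two scores, which ANCOVA on observed pairs does not.

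If results already exist, leave the planned analysis in place and report the adjusted model beside it, labelled as added.

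The cost is one model term and one error degree of freedom (126 to 125 in the three-arm model), with no new data. The baseline–post correlation and both SDs should be reported, so that readers can see the actual gain.

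### The planned repeated measures ANOVA analyses only participants with both questionnaires, and the plan states no analysis population or missing-data method

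*Combined protocol and SAP*

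**What the plan says.** The Statistical Analysis Plan states that for each primary and secondary outcome "we ran separate repeated measures ANOVAs using SPSS", and that "Differences in change over time between groups were assessed using the time-by-condition interaction term". The pooled gratitude comparison uses the same method: "we ran separate repeated measures ANOVAs comparing the CG group to the control condition".

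There are two measurement times. Under Measures, "Hedonic well-being, eudaimonic well-being, and overall well-being were assessed at baseline and post-intervention", and the secondary outcomes follow the same schedule. Under Participants and Procedure, "Participants were emailed their post-intervention questionnaire two weeks after they received their baseline questionnaire". The same section gives the number of exercises: "In total, participants were instructed to complete six condition-specific lists".

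The documents give 129 enrolled. They do not give an allocation ratio, an expected or observed attrition rate, an analysis population, a rule for missing scores or a sensitivity analysis. Apart from the outcome tests, the only comparison of the arms is on demographics at baseline.

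**The concern.** With two time points, the time-by-condition test is a one-way ANOVA on change scores. Change cannot be computed without both values, so a standard repeated measures ANOVA leaves out anyone who did not return the post-intervention questionnaire, along with the baseline score already collected. Anyone randomised who never returned a baseline questionnaire is lost as well.

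The result then describes responders. It carries over to the randomised groups only if response is unrelated to baseline and to change, or is related to them in the same way in every arm. If response depends on baseline differently across arms, regression to the mean produces a spurious interaction. A comparison of baseline demographics among those enrolled cannot reveal this.

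The introduction gives some reason to consider the possibility here: "Being motivated to first begin, and then continue to put effort into, a positive intervention can enhance intervention benefits". The GE arm is reminded of benefits at every list and the GNE arm is not. People who lose interest in the lists may also be less likely to return the last questionnaire.

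**Working it through.** The plan has no figure to reproduce: it states no power, alpha, effect size, SD or attrition. What follows is illustration.

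**Inputs.** From the documents: 129 enrolled, three arms, two time points. Assumed: equal arms (129/3 = 43), two-sided 5% test, baseline-post correlation r = 0.6, outcome SD 1 at both times, and no true effect unless stated.

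**1. Numbers analysed.** Complete cases = 129 × (1 − d). This gives about 123, 116, 103 and 90 at d = 5%, 10%, 20% and 30%.

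**2. Noise in a pairwise contrast.** SD of change = √(2(1 − 0.6)) = 0.894. The standard error is 0.894 × √(2/43) = 0.19 with no loss and 0.894 × √(2/34.4) = 0.22 with 20% loss.

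**3. Loss unrelated to baseline and change.** There is no bias even when the rates differ by arm. Simulation with control/GE loss of 15/5%, 25/10% and 30/10% gave bias of at most 0.005 SD of change and type I error of 4.4% to 4.8%. The only cost is precision.

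**4. Loss related to baseline.** Take 20% loss with a log-odds slope of 1 per SD of baseline. The responders' mean baseline then shifts by about 0.175 SD. False change in that arm = (1 − r) × shift = 0.4 × 0.175 = 0.07 SD.

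| Pattern of loss (20% per arm) | False change difference | Two-arm type I error |
|---|---|---|
| Baseline-related in one arm only | 0.07 SD | about 6% |
| Opposite directions in two arms | 0.07 + 0.07 = 0.14 SD | about 9.5% |
| Same direction and strength in both arms | 0 | about 5% |

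A normal approximation agrees. For one arm, 0.07/0.216 = 0.32 standard errors, which gives 6.2%. For opposite directions, 0.14/0.216 = 0.65 standard errors, which gives 9.9%.

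The plan tests the three-arm interaction first. With opposite directions in GE and GNE, the error of that test is about 8% to 9%. The error of CG versus control is about 5.3% to 5.4%, because the two shifts cancel in the pooled group.

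**5. What a mixed model does in step 4.** At 43 per arm, a likelihood-based model on all available scores reduces the 0.07 and 0.14 SD to about 0. The SD of the contrast is about 0.21 to 0.22 for both methods, so no precision is lost.

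**6. Loss related to stopping the lists.** Assume:
- early stoppers do 2 of 6 lists and make up 30% of GNE and 15% of GE;
- a full course is worth 0.40 SD, in proportion to lists done, so stoppers gain 0.40 × 2/6 = 0.133 SD;
- stoppers respond at 40% and others at 95%;
- the control has no effect.

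Mean gain in all randomised:
- GNE: 0.30 × 0.133 + 0.70 × 0.40 = 0.32
- GE: 0.15 × 0.133 + 0.85 × 0.40 = 0.36
- GE − GNE: 0.04

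Mean gain in responders:
- GNE: (0.12 × 0.133 + 0.665 × 0.40)/0.785 = 0.359
- GE: (0.06 × 0.133 + 0.8075 × 0.40)/0.8675 = 0.382
- GE − GNE: 0.022

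The bias in GE − GNE is about 0.02 SD, under a tenth of the standard error. In GNE − control it is 0.359 − 0.32 = 0.04 SD, about a fifth.

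**7. Loss related to the change itself.** Assume a log-odds slope of 1.5 per SD of change, those who gain least leaving most, and the unequal rates of step 3. The bias in GE − control is 0.12 to 0.21 SD of change, against GE, and type I error is 8.6% to 15.6%. Adjusting for baseline still leaves 0.10 to 0.17 SD of change and 7% to 13%.

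**The case against.** **The size is unknown.** No attrition figure is given, and with complete follow-up there is no problem. This stands. Every number above is conditional on assumptions, and the larger ones need patterns for which the documents give no evidence, such as high scorers leaving one arm and low scorers another.

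**The retention measures are the same in every arm.** The questionnaire reminder and the substitution for a class assignment apply to all conditions. The last questionnaire is not described as depending on lists completed. This makes large differential loss less likely. It does not make response unrelated to baseline or engagement.

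**A reader might infer that the trial's own mechanism predicts retention to depend on arm.** The documents do not support that. The introduction links motivation and effort to benefit and separately reports that encouraging information improved outcomes. It says nothing about returning questionnaires. The hypothesis is framed through mindset and the placebo effect, not through persistence. Differential loss is plausible, no more.

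**A reader might also infer from step 6 that the responder analysis hides half of the GE effect.** The ratio is about half only because that scenario gives the messages no direct effect, so the true difference is 0.04 SD. The absolute bias would not change a conclusion at this sample size.

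**The ANOVA sentence does not exclude prior imputation.** That is correct, but a plan is where such a step would be stated, and none is.

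**Conclusion.** The point holds as a gap in the plan with a plausible but unquantified consequence. The analysis as written uses only participants with both questionnaires, and nothing in the documents sets a population or handles missing scores.

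Under the assumptions in step 4, baseline-related loss that differs by arm gives a false change difference of 0.07 SD (one arm) to 0.14 SD (opposite directions, extreme), with two-arm type I error of about 6% to 9.5%. If loss is unrelated to baseline and change, or equally related in all arms, the bias is nil. Loss that follows the change itself could do more harm, and no adjustment for baseline fully removes it.

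The change is worth making because a method at least as good is available at almost no cost. It is not evidence that the trial's results are biased.

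**What to change.** Replace the repeated measures ANOVA as the main analysis with the following:

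- **Population.** All randomised participants with a baseline questionnaire, in their assigned condition, whether or not they kept making lists.
- **Main model.** A linear mixed model (SPSS MIXED, unstructured covariance) on all available baseline and post-intervention scores, for both the three-arm time-by-condition test and the CG-versus-control test.
- **Sensitivity 1.** The responder-only repeated measures ANOVA as now written.
- **Sensitivity 2.** Multiple imputation with a small model (that outcome's baseline, condition and number of lists submitted), followed by a delta shift of the imputed scores. This addresses loss linked to stopping the lists or not at random.
- **Reporting.** By condition: the post-intervention response, the lists submitted and the number randomised without a baseline questionnaire.

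The imputation model should stay small and secondary. About 35 responders per arm (34.4 at 20% loss) will not support separate models by arm using the baselines of all outcomes. The hedonic, eudaimonic and overall scores also overlap, since they come from the same 14 items.

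The cost is SAP wording and some extra analysis in the same software, on data that the online forms should already hold. The downside is small: the mixed model assumes data are missing at random given baseline. It does not correct for loss driven by stopping the lists, which is why the second sensitivity analysis is needed.
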